## **D. Design and Methods**

### **(1) Study Design**

We propose a single arm, open label, interventional study to compare the opiate requirements of 45 patients who consent to receive BESB catheters following cardiac surgery via sternotomy versus 90 matched historical controls who had similar surgical procedures but without BESBs.

Patients meeting eligibility criteria will be recruited and enrolled to have BESBs placed for postoperative pain control as a part of their perioperative anesthetic

plan. These patients will subsequently have a variety of preoperative demographic and functional data collected as well as data related to their surgeries and postoperative course all collected for later analysis. This enrolled group of patients will subsequently be compared regarding these outcome measures with a 1:2 matched, retrospective analysis of patients in the cardiac surgical ERAS program who did not receive regional blocks as a component of their anesthetic care. (The ERAS Cardiac program is a heart center perioperative evidence-based quality initiative. Retrospective data analysis of outcomes for patients in this program is performed for quality improvement purposes and outcomes research [IRB P00029161 – PI: [name] MD, co-investigators: [name] MD, [name] MD]). Children aged 2 years through 17 years meeting entry criteria will be screened and recruited for participation from the Boston Children's Hospital cardiac surgical program.

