### **Secondary:**

- Analgesic requirements, rendered as total opiate equivalents, at 12, 24 and 48 hours, and the 24-hour period preceding both 72 and 96 hours postoperatively.
- Duration of intubation following OR exit.
- Duration of ICU stay following OR exit.
- Duration of inpatient admission.
- Median pain scores collected per standard of care (VAS, NRS, INRS, or FLACC) at 0-3h, 3-6h, 6-12h, 12-24h, 24-36h and 36-48h.
- Incidence of postoperative nausea and vomiting during the following time ranges: 0-6h, 6-12h, 12-24h, and overall
- Time to mobilization (e.g. up to chair, ambulation).
- Quality/Quantity of mobilization and sleep via postoperative actigraphy.
- Outcome and satisfaction measures associated with routine perioperative questionnaire responses.
- Adverse events. – catheter, hemodynamic instability during placement (new inotrope or vasopressor – including Ca, volume > 5ml/Kg, variation 10% baseline SBP and MAP)
- All major Society of Thoracic Surgeons (STS) standard indices of morbidity and mortality

\*Of note, all of the above data points are collected automatically (via the electronic medical record) for all patients, as a part of their routine clinical care, regardless of whether or not they participate in the study.

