## **I. Adverse Event Criteria and Reporting Procedures**

Adverse or unanticipated events will be reported as required to the Boston Children's Hospital IRB by the PI according to institutional reporting requirements.

An Adverse Event refers to any untoward medical occurrence whether or not it is considered intervention-related.

As noted above, analysis of the retrospective outcomes data for the 45 BCH patients treated with ESBs, the patients in our trial study, and the national and international literature demonstrates no evidence that this block type is associated with any greater risk than that demonstrated by aggregate block data from the various pediatric regional anesthesia registries. Information currently available suggests that regional blockade (including the erector spinae block), when performed properly, carries a very low risk of morbidity and mortality in appropriately selected infants and children.

Nevertheless, as there exist little prospective outcomes data related to the ES block, we will implement a rigorous system to follow and report any adverse events, including interim analyses by a non-blinded statistician, as described below:

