## **K. Data Analysis Plan**

At the time of data analysis, de-identified datasets will be downloaded from the secure database and merged into secure statistical analysis tool for purposes of analysis. Missing data will be accounted for when the data is coded into respective variables.

Descriptive statistics will be generated in order to summarize demographic characteristics of patients enrolled. Data will be tested for normality using the Shapiro-Wilk test. Data will be presented as total n (%), means and standard deviations (SD) if the distribution appears normal, or medians and range when not.

Assuming normality, t-tests will be conducted to investigate the differences between the two exposure groups (to compare total opioid equivalents, time required to place the block, time to extubation, and time to discharge, etc.). If data does not appear to be normal, Wilcoxon Rank Sum/Mann-Whitney tests will be used for group comparisons. Repeated measure analysis will be used to compare pain scores over time between groups and when compared to baseline values. Adverse events and complications (if any) associated with the blocks will be recorded and categorized. Fisher's exact test will be used to compare the proportion of patients who reported adverse events between the two groups.  $P<0.05$  will be considered statistically significant.

Should a clinically significant effect be demonstrated, healthcare costs related to the surgical encounter for both groups will be approximated and compared in order to better assess the added value of the intervention in a more global fashion.

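### Does Section K need changing because it lists block-placement time as a two-group test and does not name the adverse events that enter the between-group Fisher test?

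*Combined protocol and SAP*

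**What the plan says.** Section K names t-tests, or rank-sum tests if the data are not normal, for differences between the two exposure groups, "to compare total opioid equivalents, time required to place the block, time to extubation, and time to discharge". Section D(1) describes the comparison group as "matched historical controls who had similar surgical procedures but without BESBs".

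On safety, Section K has two consecutive sentences. The first says that adverse events and complications "associated with the blocks will be recorded and categorized". The second says that Fisher's "exact test will be used to compare the proportion of patients who reported adverse events between the two groups".

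Two other sections bear on what an adverse event is. The adverse-event bullet in Section E (Secondary) mentions catheter events and "hemodynamic instability during placement (new inotrope or vasopressor", with further criteria including "variation 10% baseline SBP and MAP". A footnote to that list says that "all of the above data points are collected automatically (via the electronic medical record) for all patients". Section I defines an adverse event as "any untoward medical occurrence whether or not it is considered intervention-related".

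The last paragraph of Section B plans to evaluate adverse events between the groups. Aim 1 in Section A assesses BESB complications, and Aim 3 compares postoperative complications, readmissions and mortality between the groups.

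**The concern.** Placement time exists only in patients who had a block, so a two-group test of it has no control data.

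The Fisher test raises a subtler question. A control cannot have a catheter problem or become unstable during a placement that never took place. If the Section E bullet supplied the event set, the control count would be zero by design. The p-value would then depend only on the BESB count, and a significant result would show only that one group had catheters. The Section E footnote does not remove this, because collecting data on controls cannot give them a placement event.

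If the broad Section I definition applied, one pooled count would mix harm from the block (Aim 1) with complications that either group can have (Aim 3). A null result could then sit beside real block harm. The plan does not state which definition it means, and in an open-label comparison with historical controls a choice made after the data are seen would be open to criticism.

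**Working it through.** **Plan's own figure.** The plan gives no calculation for the adverse-event or placement-time tests. Its only design calculation, in Section L, is for square-root 96-hour opioid use (difference 0.18, SD 0.32, 1:2 ratio, two-sided 0.05, 80% power):

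n(BESB) = 1.5 × (1.96 + 0.8416)² × 0.32² / 0.18² = 1.5 × 7.849 × 3.1605 = 37.2, so 38, with 76 controls. This agrees with the plan and involves no adverse-event input.

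**Reading A: only catheter and placement events count.** Group sizes are 45 and 90 (Section L). With no control events, all x affected patients are in the BESB group. That is the least likely split of x, so the two-sided Fisher p-value is C(45, x) / C(135, x).

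| x of 45 | Calculation | p |
|---|---|---|
| 1 | 45/135 | 0.333 |
| 2 | (45×44)/(135×134) = 1,980/18,090 | 0.109 |
| 3 | (45×44×43)/(135×134×133) = 85,140/2,405,970 | 0.035 |
| 4 | 3,575,880/317,588,040 | 0.011 |

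Three events are enough for p < 0.05. At 38 versus 76 the threshold is the same: (38×37×36)/(114×113×112) = 50,616/1,442,784 = 0.035.

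The chance of reaching it is P(X ≥ 3) with X ~ Binomial(45, q).

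| Block-only rate q | Source | P(X ≥ 3) |
|---|---|---|
| 0.93/1000 | neurologic symptoms, Section C | about 1 in 90,000 |
| 2% | assumed | 6% |
| 5% | assumed | 39% |
| 10% | one kinked but useable catheter in 10 pilot patients, if counted | 84% |

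The exact 95% interval for 1/10 is 0.3% to 44.5%, so the last row is weakly supported. The documents give no rate for the placement criteria.

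**Reading B: the Section I definition.** Assume a 10% rate of events that either group can have and a 10% block-only rate. The BESB rate is 1 − 0.9 × 0.9 = 19%, against 10% in controls. Exact enumeration gives 27% power to detect that true excess. With no block-only events the test rejects about 3% of the time, so the pooled test is valid, though weak at these rates.

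**Which reading fits.** Section K separates block-associated events, which are described, from adverse events without that qualifier, which are compared. Section I has the protocol's only formal definition, and it is broad. Section B and Aim 3 announce a general comparison. On the other side stands one telegraphic bullet in Section E, in a list that gives nausea and vomiting and STS morbidity and mortality as separate endpoints open to both groups. The balance favours Reading B, with block events also described separately.

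**What a reader would see.** Aim 1 and the n (%) presentation in Section K already provide for block events in the BESB group. An exact interval would add, for example, an upper limit of 7.9% for 0/45, or 1.4% to 18.3% around 3/45 = 6.7%. The interval follows directly from the reported count.

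**The case for a change.** The strongest case for acting is that the text is open, the choice can decide a p-value, and one or two sentences would settle it. The two consecutive sentences in Section K do not expressly keep block events out of the Fisher test. Three catheter events would be significant under Reading A, while under Reading B a real excess could well be missed.

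Part of this stands. Placement time is misplaced in the list, and no passage names the event set. The Fisher figures are correct.

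The consequences are smaller than they seem. A significant result under Reading A would reflect real block events and count against BESB, so it could not support a false claim of safety. The 27% under Reading B is power at two assumed rates. It describes a small sample rather than a bias caused by the wording, and the separate account of block events limits how far a null pooled result could hide harm.

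Replacing the pooled test by tests of several named events would also have a cost. It would give up a legitimate question about net harm and add comparisons, and nausea and vomiting and STS outcomes are endpoints already.

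**Conclusion.** No change follows. The placement-time entry is a clerical slip: the test cannot be run, and an analyst would summarise the time in the BESB group only. The unnamed event set is a gap that an analyst would fill sensibly from Sections A, B, I and K, by describing block events in the BESB group and comparing general adverse events between groups.

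The threshold of three events in 45 (p = 0.035) is exact but conditional on the less natural reading. The chance of reaching it runs from about 1 in 90,000 to 84% across rates that are mostly assumed, so it does not measure an expected error. Stating the event set and adding an exact interval would be tidy, but would add little to what is already planned. The primary endpoint, the 38/76 sample size and the Section I stopping rules do not use this test. This conclusion assumes that block events are in fact reported separately, as Aim 1 and Section K indicate.

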Recently, the erector spinae block (ESB) has become popular for providing analgesia after a number of anterior chest and abdominal procedures. This simple interfascial plane block can reliably provide unilateral chest and/or abdominal wall analgesia. It has been described in numerous case reports and case series as an effective block for management of unilateral thoracotomies, unilateral rib fractures, unilateral abdominal incisions and most notably, for management of post-sternotomy pain when applied bilaterally. New case reports and series involving the ESB are being published almost weekly with a growing number of manuscripts specific to cardiac surgical applications. Indeed, numerous randomized controlled trials have investigated the analgesic efficacy of bilateral erector spinae plane blocks (BESB) compared with

conventional treatment for pain after cardiac surgery in adult patients and have been published recently (2018-2019) with promising results.

As an interfascial plane block in a compressible anatomical space, the ESB is considered safe in anticoagulated (or recently anticoagulated) patients. It is fast becoming a preferred anesthetic option at BCH for anticoagulated patients - as opposed to neuraxial (e.g. epidural) and paraneuraxial blocks (i.e. paravertebral) nerve blocks, which are largely contraindicated in this setting. Further, given its relative ease of placement, apparent efficacy and safety profile, it is increasingly becoming a standard option for patients undergoing a wide range of thoracic, abdominal and thoraco-abdominal procedures.

We are fortunate at BCH to have the largest pediatric cardiac surgical program in the United States. We also have an active, and well organized regional anesthesia service. We are in a unique position to more thoroughly evaluate the effectiveness and safety of regional anesthetics in children following cardiac surgery. Furthermore, we feel it is critical that institutions such as BCH take a leading role in documenting the effects of regional anesthesia on the most important outcome measures when considering perioperative medicine. These include: overall pain management, surgical healing, functional recovery, long term pain symptoms, and emotional/behavioral outcomes after surgery.

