As previously noted, our group recently investigated the feasibility of performing BESBs in a pediatric cardiac surgical population undergoing sternotomy-based procedures at this institution. At the conclusion of this 10-patient pilot, we found that performing these blocks was technically feasible -- requiring 30 minutes or less of OR time -- and resulted in an approximate 25% reduction in rescue opioid requirements in the first 48 hours amongst the BESB group ( $p=0.048$ ). There were no significant adverse events noted during this pilot with the exception of a single instance of a kinked (but useable) catheter.

While the numbers at BCH are relatively small, retrospective analyses of ESBs performed in this institution in non-cardiac surgery have demonstrated no evidence that this block type is associated with any greater risk than that demonstrated by aggregate block data from the various pediatric regional anesthesia registries. Information currently available suggests that regional blockade, when performed properly, carries a very low risk of morbidity and mortality in appropriately selected infants and children. Furthermore, we have found no evidence of increased adverse events present in the ESB patients when compared to patients receiving other regional anesthetics in our local analysis. Indeed, two abstracts addressing the safety and efficacy of ESB blocks in BCH patients have recently been accepted for presentation at the major regional anesthesia conference.

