## **L. Sample Size Considerations**

In order to evaluate the efficacy of BESB in this cardiac surgical population compared to those who did not receive blocks, we have defined 'efficacious' as denoting an at least 15% difference in the total opioid consumption at 96hours based on the historical rescue opiate data in the matched cohort. Assuming an alpha of 5%, 80% power, and the mean opiate requirements found in our pilot study, we estimate that a total sample size of 38 patients undergoing sternotomy with BESBs and 76 matched controls are needed to demonstrate efficacy of the new treatment (BESB).

**Table 1** (below) demonstrates that, using a 1:2 ratio of BESB:standard ERAS patients, 38 BESB and 76 standard ERAS patients are required to detect a 0.18 mean difference (15% relative reduction associated with BESB) in square-root Total (96-hr) OME between groups with 80% power using a two-sided 0.05-level test. Because the coefficient of variation for 48-hour OME is somewhat smaller, this sample size will provide 87% power to detect a 15% relative reduction (0.16 mean difference) in square-root 48-hr OME between groups using a two-sided 0.05-level test.

Because the larger SD of the two groups from background data (see **Table 2**) was used in these calculations, and because the groups will be matched on several patient characteristics which will minimize variation, these assumptions are conservative and power to detect the effect sizes shown in Table 1 may be even higher than shown.

**Table 1. Required Sample Size to Detect BESB vs. ERAS Group (1:2 Ratio) Reductions in 48- and 96-hour OME (square-root transformed) assuming two-sided  $\alpha=0.05$ , 80%/85% Power, 48-hour mean sqrt OME 1.05 and 96-hour mean sqrt OME 1.23 in ERAS Group.**

Outcome (sq. root)	SD	%Reduction	Group Difference	Power	BESB N	ERAS N
48 hr OME	0.26	15%	0.16	80%	32	64
48 hr OME	0.26	15%	0.16	85%	36	72
48 hr OME	0.26	20%	0.21	80%	19	38
48 hr OME	0.26	20%	0.21	85%	21	42
96 hr OME	0.32	15%	0.18	80%	38	76
96 hr OME	0.32	15%	0.18	85%	43	86
96 hr OME	0.32	20%	0.25	80%	20	40
96 hr OME	0.32	20%	0.25	85%	23	46

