**Table 2. Background Data**

Group	N	Obs	Variable	N	Mean	Std Dev	Median
ERAS	20	sqD0N0D1N1	20	1.050	0.181	1.049	
		sqtotolome	20	1.231	0.211	1.227	
		D0N0D1N1_OME	20	1.134	0.390	1.100	
		Total_OME	20	1.557	0.540	1.505	
BESB	10	sqD0N0D1N1	10	0.890	0.261	0.898	
		sqtotolome	10	1.120	0.320	1.157	
		D0N0D1N1_OME	10	0.854	0.528	0.810	
		Total_OME	10	1.346	0.724	1.340	

Given the possibility of patient withdrawal due to procedural changes, intraoperative exclusionary events, etc., we plan to enroll 45 patients for the BESB intervention group and 90 matched historical controls from the cardiac ERAS database (IRB P00029161).

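### The only inferential analysis of adverse events is a between-group Fisher test without an interval, which is a poor readout for the aim of assessing block complications

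*Combined protocol and SAP*

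**What the plan says.** Section K of the combined protocol and SAP gives one inferential method for adverse events: Fisher's "exact test will be used to compare the proportion of patients who reported adverse events between the two groups", with P<0.05 as the threshold for significance. Events associated with the blocks are otherwise to be recorded and categorised, and data in general are to be presented as n (%). No interval, upper limit, acceptable rate or power is given for safety.

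Section L sizes the trial on opioid consumption only, "using a two-sided 0.05-level test". After an allowance for withdrawals, "we plan to enroll 45 patients for the BESB intervention group and 90 matched historical controls".

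Safety is nonetheless part of the purpose. Aim 1 in section A includes complications related to the block, and section E lists adverse events as a secondary outcome, naming catheter events and haemodynamic instability during placement. The Background describes the institution as well placed to "evaluate the effectiveness and safety of regional anesthetics in children following cardiac surgery".

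Section I adds count-based halting rules, an independent review of each cohort of 15 patients, and interim analyses by a statistician for which no method is given.

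**The concern.** A between-group P-value is not an estimate. For complications of the block itself, the question in Aim 1 is how often they occur and how high the true rate could be. A comparison with patients who had no block does not answer that, because their rate is zero by construction. For complications that either group can have, a non-significant result at this sample size cannot separate no added risk from too few patients.

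At stake is what the final report can say about complications. Section N says the results may lead to a randomised trial. Its planners would need an event rate and its uncertainty, and section K does not promise the second. There is also some risk of misreading, since earlier sections already reason from absence of evidence: section C says "we have found no evidence of increased adverse events present in the ESB patients", and section I says the available data "demonstrates no evidence that this block type is associated with any greater risk".

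**Working it through.** **Inputs.** From the documents: 45 vs 90 planned and 38 vs 76 required (section L); Fisher's exact test at P<0.05 (section K). Section K does not state sidedness for this test, so I take it as two-sided, as in section L. Assumed: control event rates, because the documents give no overall adverse-event rate for this population.

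**1. The plan's own figures.** These concern opioid use, and they reproduce.
- 96 hours, difference 0.18, SD 0.32, ratio 1:2: n = 1.5 × (1.960 + 0.842)² × 0.32² / 0.18² = 37.2, so 38 BESB and 76 controls.
- 48 hours at 38 vs 76: 0.16 / (0.26 × √(1/38 + 1/76)) = 3.10, and Φ(3.10 − 1.96) = 87%, as stated.

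There is no corresponding figure for adverse events.

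**2. Events that only blocked patients can have.** With no events in 90 controls, the Fisher P-value for a events in 45 is C(45,a) / C(135,a).
- a = 2: (45 × 44) / (135 × 134) = 0.109, not significant.
- a = 3: 0.035, significant.

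Significance therefore needs at least 3 events. The chance of 3 or more among 45 is 39% if the true rate is 5% and 84% if it is 10%. A doubling has no meaning here, since the control rate is zero.

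The exact (Clopper-Pearson) two-sided 95% upper limit describes the same data directly:
- 0/45: 1 − 0.025^(1/45) = 7.9%
- 2/45: 97.5% quantile of Beta(3, 43) = 15.1%
- 0/38: 1 − 0.025^(1/38) = 9.3%

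**3. Events possible in both groups.** Power is the sum, over all tables with two-sided Fisher P<0.05, of Bin(a; n₁, 2p) × Bin(b; n₂, p), where p is the control rate and the BESB rate is twice that. The miss rate is 1 − power.

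| Control vs BESB rate (assumed) | Power, 45 vs 90 | Missed, 45 vs 90 | Missed, 38 vs 76 |
|---|---|---|---|
| 5% vs 10% | 17% | 83% | 85% |
| 10% vs 20% | 32% | 68% | 73% |
| 15% vs 30% | 48% | 52% | 58% |
| 20% vs 40% | 64% | 36% | 43% |

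Outside that band, at 45 vs 90, the miss rate is 97% for 1% vs 2% and 9% for 30% vs 60%.

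For scale, 80% power by the usual normal approximation needs about 144 + 288 patients for 20% vs 10% (158 + 316 with continuity correction), and about 60 + 120 for 40% vs 20% (67 + 134).

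**The case against.** The strongest reply is that the plan never draws the inference at issue. A reader might infer that P>0.05 will be reported as evidence of safety; no section says so. The hypothesis is about efficacy, adverse events are one secondary outcome, and low power for safety is usual in small trials sized on efficacy. Section I also acknowledges that prospective data on this block are scarce, and its favourable statement draws on published literature and registries as well as local patients. All of this stands. The gap is a missing estimate, not a stated error.

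A reader might also infer that the Fisher test is the only safety criterion. It is not. Section I halts enrolment on any one listed serious event, on more than 2 minor or moderate events in a patient, or on more than 10 in aggregate. If the events were those minor ones, one per affected patient, the chance of more than 10 in 45, from Bin(45, p), is 84% at a 30% rate and 99% at 40%. In those scenarios a halt would usually precede the final test. At 20% the chance is 28%, and the rule does not cover other event types. These rules protect patients during the trial; they do not say how the final risk will be estimated.

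Finally, 36% to 83% might be taken as a property of the design. It is not: it follows from assumed control rates of 5% to 20%, and the step 3 figures for rarer and commoner events show that it is not a bound.

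**Conclusion.** The point holds as a minor one. Fisher's test is the only inferential safety analysis, though not the only safety provision, and it is a poor readout for Aim 1. For catheter and placement events this needs no assumed control rate, because controls cannot have them: 2/45 vs 0/90 is not significant, yet it leaves block-related rates of up to 15.1% compatible with the data. For shared events, the size of the problem depends on the assumed control rate and on a two-sided test. Within 5% to 20%, a doubling is missed in 83% down to 36% of trials at planned enrolment, and in 85% down to 43% at the required sample. The problem is worse for rarer events and small for common ones. The documents do not support saying that the plan treats non-significance as proof of safety. The primary outcome is unaffected.

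**What to change.** In section K:

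- (a) For block-related complications, report the BESB-arm rate with an exact Clopper-Pearson two-sided 95% interval.
- (b) For complications possible in both groups, report the risk difference with a 95% interval, and keep Fisher's test only as a supplementary result.
- (c) State that a non-significant result will not be read as no added risk.

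This takes a few sentences, with no new data, no added patients and no clinical change. The one downside is a slightly less favourable safety statement: after no events in 45 patients, for example, the report would say that the upper limit for the rate is 7.9%, rather than that no difference was found.

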#### Specific Aims:

1. Evaluate the utility of BESB in cardiac surgical patients by assessing the pain scores, opioid consumption, and complications related to BESB.
2. Compare intra- and postoperative opioid use in patients receiving BESB vs. matched historical controls who did not receive BESB in the ERAS program.
3. Compare clinical outcomes between the 2 groups: duration of mechanical ventilation, time to mobilization, pain scores (median pain score per period), intensive care unit length of stay (LOS), incidence of postoperative nausea and vomiting, postoperative complications, hospital LOS, readmissions, mortality, recovery to baseline activity and sleep post discharge, total and rescue opioid pain medication requirements.
4. Evaluate quality of sleep and activity with (Fitbit™) smart watch device of patients receiving BESB during the postoperative period.

**Hypothesis:** The investigators hypothesize that BESB is efficacious with respect to pain control and will lead to a 15% or greater reduction of consumed opiate equivalents at 12, 24 and 48 hours, and the 24-hour period preceding both 72 and

96 hours postoperatively compared to matched historical controls who received standard of care pain management (systemic opioid therapy).

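### Section K applies one per-test P<0.05 significance rule to roughly 9 to 12 non-opioid secondary comparisons, with no hierarchy, adjustment or exploratory label

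*Combined protocol and SAP*

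**What the plan says.** Section K plans t-tests or Wilcoxon rank-sum tests for an open-ended list of outcomes, a repeated-measures analysis of pain scores, and Fisher's exact test for adverse events. One decision rule closes the paragraph: P<0.05 "will be considered statistically significant". Nothing restricts that rule to the primary outcome.

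The outcomes it can reach are listed in two places. Specific Aim 3 opens "Compare clinical outcomes between the 2 groups: duration of mechanical ventilation, time to mobilization, pain scores (median pain score per period" and continues through ICU and hospital stay, nausea and vomiting, complications and other outcomes. The secondary list in section E repeats most of these. It includes "Incidence of postoperative nausea and vomiting during the following time ranges: 0-6h, 6-12h, 12-24h, and overall" and "All major Society of Thoracic Surgeons (STS) standard indices of morbidity and mortality".

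Neither place puts the secondary outcomes in order of importance. The documents contain no alpha allocation, no multiplicity adjustment, no condition that the primary comparison succeed first, and no statement that the secondaries are exploratory or descriptive. Section L fixes the test level only for the sample-size calculation, "with 80% power using a two-sided 0.05-level test".

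Two other statements bear on the point. Sections B and L define efficacy as a 15% difference in opioid use. Section N says the results may help in developing a later randomized trial.

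**The concern.** A rule that calls each P<0.05 significant does little harm on one test. Applied to about a dozen secondary outcomes on the same footing as the primary, it makes at least one chance finding fairly likely. Followed literally, it lets the report describe a shorter time on the ventilator, a shorter ICU or hospital stay, or less PONV as a statistically significant benefit of BESB on one unadjusted P value, even when the opioid comparison is null.

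Such a statement could influence practice or the endpoint chosen for the later trial mentioned in section N. Because the study is open-label with historical controls, an isolated secondary P value is already weak evidence, and the plan's wording gives it more standing than it should have.

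The point concerns only the non-opioid secondaries. How the several opioid windows are handled is a separate question.

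**Working it through.** **1. The plan's own figures.** The documents give no family-wise error rate, so the figures to reproduce are those in section L. They show what level each test is run at.

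- 96-hour OME: "38 BESB and 76 standard ERAS patients are required to detect a 0.18 mean difference" with SD 0.32. SE = 0.32 × √(1/38 + 1/76) = 0.0636. Power = Φ(0.18/0.0636 − 1.96) = Φ(0.871) = 0.81, against 80% stated.
- 48-hour OME: "this sample size will provide 87% power to detect a 15% relative reduction (0.16 mean difference") with SD 0.26. SE = 0.26 × √(1/38 + 1/76) = 0.0517. Power = Φ(0.16/0.0517 − 1.96) = Φ(1.137) = 0.87, as stated.

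Both reproduce at two-sided 0.05 for a single test. That is a per-test level: 0.05 in either direction, 0.025 in favour of BESB. The sample size is not affected by this point.

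**2. Count of non-opioid between-group comparisons** (section E secondary list, with the methods in section K):

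| Outcome | Tests |
|---|---|
| Duration of intubation | 1 |
| ICU stay | 1 |
| Hospital stay | 1 |
| Pain scores (one repeated-measures comparison) | 1 |
| PONV (three windows plus overall) | 4 |
| Time to mobilization | 1 |
| Questionnaire outcomes | at least 1 |
| Adverse events | at least 1 |
| STS morbidity and mortality indices | at least 1 |
| **Total** | **12** |

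All opioid outcomes are left out. Actigraphy is left out because section B confines it to the BESB group. Nine is used as a lower count. It corresponds, for example, to setting aside adverse events, the STS indices and one of the overlapping PONV entries.

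**3. Independent tests, all nulls true.** P(at least one) = 1 − (1 − a)^k.

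- k = 12, either direction: 1 − 0.95^12 = 0.46. In favour of BESB: 1 − 0.975^12 = 0.26.
- k = 9, either direction: 1 − 0.95^9 = 0.37. In favour of BESB: 1 − 0.975^9 = 0.20.

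**4. Correlated tests.** The outcomes come from the same patients, so independence is an upper case. Take standard normal test statistics with a common correlation ρ. With c = 1.96,

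P(at least one) = 1 − ∫ φ(x) [Φ((c − √ρ·x)/√(1−ρ)) − Φ((−c − √ρ·x)/√(1−ρ))]^k dx.

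For errors in favour of BESB only, drop the second Φ term. Numerical integration gives:

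| k | Direction | ρ = 0 | ρ = 0.5 | ρ = 0.8 |
|---|---|---|---|---|
| 12 | either | 0.46 | 0.32 | 0.19 |
| 12 | favouring BESB | 0.26 | 0.16 | 0.09 |
| 9 | either | 0.37 | 0.27 | 0.17 |
| 9 | favouring BESB | 0.20 | 0.13 | 0.08 |

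The values of ρ are assumptions, since the documents report no correlations among these outcomes.

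**The case against.** The strongest reply has four parts.

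- **No promise is broken.** Section K sets a per-test threshold, and the plan nowhere claims 5% error across the secondaries. This stands, so the inflation cannot be described as a breach of a stated level.
- **Efficacy is already tied to opioid use.** Under sections B and L, a small P value for ICU stay or PONV cannot meet the plan's own definition of efficacy. This stands and narrows the harm. It does not remove it, because section K still allows that result to be called statistically significant.
- **The tests are not 12 equal, full-size chances of a false benefit.** The adverse-event entry in section E names catheter events and instability during placement, which unblocked controls cannot have. On that definition it cannot yield a false benefit for BESB. Overall PONV contains the separate windows, and section B lists three PONV periods where section E lists four. Fisher's exact test on rare events rejects less often than 5%. Separate tests for each PONV window, the questionnaires and the STS indices are inferred from the endpoint list and the open-ended wording of section K. This stands, and it is why nine tests are shown beside twelve and why the figures are upper-side estimates.
- **Unadjusted secondaries are common, and a later trial would retest them.** That is a fair defence when the secondaries are labelled exploratory. Here they share the primary outcome's significance rule, and section N's remark about a later trial puts no limit on how they are read.

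Two tempting extensions also fail. Counting pain by its six listed windows would give 17 tests, but section K plans one repeated-measures analysis of pain. Block placement time, which section K lists among its group comparisons, has no counterpart in the controls and is not counted here.

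**Conclusion.** The concern holds in a limited form. Section K gives every between-group test the same significance rule, and roughly 9 to 12 non-opioid secondaries fall under it with nothing to separate confirmatory from exploratory results. With 12 true nulls and full-size tests, the chance of at least one nominally significant secondary is about 19% to 46% in either direction, or 9% to 26% in favour of BESB. With nine it is about 17% to 37%, or 8% to 20%. The conservative Fisher tests and overlapping PONV windows pull these figures down.

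A reader might infer that the study carries a 32% chance of a false secondary claim for BESB where it promised 5%. The documents do not support that. The 32% needs 12 tests and a correlation of 0.5 that no section supplies, and it counts errors against BESB as well. In favour of BESB the same assumptions give 16%, to be set against 2.5% per test. The 5% in section K is a per-test level, not a family-wise one.

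The consequence is confined to isolated secondary findings being reported as significant benefits. The efficacy definition and the sample size are unaffected. Multiplicity control would not address confounding from the historical controls.

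**What to change.** In section K, limit the P<0.05 declaration to the primary comparison, and add a statement to this effect:

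> The secondary endpoints in section E are exploratory. They will be reported as between-group differences with 95% confidence intervals, not adjusted for multiplicity, and no claims of statistical significance will be made for them.

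If the investigators want a formal claim on a few secondaries, for example intubation time, ICU stay and hospital stay, they should name them in advance. Those would be tested in a stated fixed order at 0.05, only after the primary comparison is significant, stopping at the first non-significant result.

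The exploratory label should not extend to the safety monitoring and halting rules in section I, which stay as they are.

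The cost is two sentences, with no extra patients or data. The one downside is that an isolated secondary P<0.05 can no longer be reported as a significant benefit.
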